Male and female lay leaders will be selected based on being a community leader, having a heart for healing and reconciliation in the Somali community, and willingness to later train additional group leaders. Lay leaders will be able to speak and read in both Somali and English. All lay leaders will sign contracts to be individual investigators affiliated with their respective universities. Lay leaders will attend two, 4-hour training sessions (approximately 6 hours actual training, allowing time for arrival and prayer times), where they will receive the manual and an overview of the program, review and practice components of group sessions, and identify potential issues and problem solve. Lay leaders will be volunteers.

Group participants will be recruited through flyers and word of mouth by the lay leaders, community and faith leaders, and self-referral, focusing on those in need of trauma healing based on their report of re-experiencing and/or avoidance of traumatic events. All participants will sign informed consent forms, in either Somali or English depending on their language preference. Randomization to active or waitlist will be conducted using a 1:1 ratio, allowing for individuals or clusters of up to three individuals being randomized as a unit. Questionnaires will be completed prior to the start of group (Session 1), middle (Session 3), and end (Session 6), with a three-month follow up for individuals in the RCT using a Qualtrics link. Participants will receive fifty dollars at the three-month follow up. Groups will meet weekly for 2 hours, with length of time varying depending on breaks for prayer. After each group, lay leaders will meet briefly with a clinical supervisor from the investigational team, either in person or on phone/online, for a discussion of the session, consultation on content or clinical issues that arose during session, and any supervisory notes. Once the six weekly sessions have been completed, a group social event will be held as a closure ceremony and to facilitate community reconciliation. The content of each group session is clearly delineated in the Islamic Trauma Healing manual.

E. Quality Control

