F. Power Analysis

We estimated sample size based primarily on Specific Aim 1. We estimated power to detect effects using G*Power and Optimal Design (for multilevel data), with $\alpha = .05$ and power $(1 - \beta) = .80$, completing 10,000 replications per analysis. With a conservative estimated dropout of 20% across conditions, though no dropout occurred in our pilot work, we will have power to detect moderate to large effects of condition on outcomes at post-treatment ($d = 0.72$) with 30 per group, and ($f^2 = 0.28$) with generalized linear models (GLM),

both large effects. For repeated measures analyses, with 4 data points, 30 per group with 20% missing data, we will be able to detect medium effects ($d = 0.60$) on change over time. These effect sizes are well below the observed effects in our pilot work ($g = 0.76$ to $g = 3.22$). For Specific Aim 2, the same power calculations for Aim 1 apply; however, tests of indirect effects are exploratory, we will be powered to detect a moderate indirect effect ($a*b = 0.25$), using the same constraints as above. To balance feasibility and ability to detect meaningful effects, we will recruit 30 individuals per treatment group

G. Analytic Strategy

Data will be screened for accuracy, missing values, and fit between the data and the assumptions of the general linear and linear mixed-model analysis (e.g., linearity, multivariate normality, independence of errors; Tabachnick & Fidell, 2007). Data transformations or model respecifications will be performed for any violated assumptions. We will implement pattern-mixture models to examine whether the missingness can be considered ignorable. For non-ignorable missing data, values will be multiply imputed and data recombined using Rubin's rules (Rubin, 1987) in the mixed model program. We will examine associations between primary dependent variables and factors such as gender, age, time since trauma, etc. and make appropriate analytic adjustments. We will test all covariate by predictor interactions to ensure our main effects are independent of the level of these putative covariates; these tests of effect modification are easily accommodated. However, we are underpowered to assess these interactions. To account for subjects being nested within groups in the treatment condition, we will co-vary treatment group using dummy codes in all analyses, as linear mixed models are difficult to estimate when the number of clusters is very small (Snijders, 2005).

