Predictor Variables: Predictor is treatment (Islamic Trauma Healing vs. WL)

Dependent Variables: Negative beliefs (PTCI), connectedness (SC; DSES), and forgiveness (TRIM-R) will be measured.

Analyses: We will conduct similar analyses to Aim 1, using both GLMs and GLMMs to obtain effect size estimates. In the GLMs, treatment will predict negative beliefs, connectedness, and forgiveness from baseline to post-treatment (controlling for baseline levels). GLMMs will be conducted as above, and treatment will be used to predict post-treatment levels and change over time in the dependent variables, to estimate how groups

STUDY PROTOCOL: A Lay-Led Intervention for War and Refugee Related Trauma: NCT03502278
July 18, 2018

differ in their rate of symptom reduction over the course of treatment.

Exploratory Hypothesis. Changes in negative beliefs (PTCI), connectedness (SC; DSES), and/or forgiveness (TRIM-R) will mediate the relationship between treatment condition and changes in PTSD and related symptoms. For the GLMs, we will predict Session 3 mediators from treatment (a path) and follow-up outcomes from the mediator (b path) controlling for treatment and baseline levels. Mediation will be tested using the product of coefficients method with bootstrapped standard errors (MacKinnon et al., 2009). In the GLMMs, we will conduct a 2-1-1 mediation, predicting the mediator at all time points from treatment (2-1), and the outcome at all time points from the mediator (1-1), controlling for treatment. This will be based on Bauer et al. (2006), generally following the product of coefficients method. It is recognized that this is underpowered.

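### Testing the exploratory indirect effect with a bootstrap standard error is usually conservative and gives up about 2 to 22 points of power against a percentile interval from the same draws

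*Combined protocol and SAP*

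**What the plan says.** In the Combined protocol and SAP, section G, Specific Aim 2, Exploratory Hypothesis, the GLM version of the mediation analysis is set up as follows: "we will predict Session 3 mediators from treatment (a path) and follow-up outcomes from the mediator (b path) controlling for treatment and baseline levels". The test is then given in one sentence: "Mediation will be tested using the product of coefficients method with bootstrapped standard errors". No reference distribution is stated, and no percentile, bias-corrected or other asymmetric interval appears anywhere in the document. The same paragraph goes on to the 2-1-1 GLMM and closes with "It is recognized that this is underpowered".

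Section F (Power Analysis) classes tests of indirect effects as exploratory but also says "we will be powered to detect a moderate indirect effect ($a*b = 0.25$), using the same constraints as above". The constraints referred to are "with $\alpha = .05$ and power $(1 - \beta) = .80", the plan that "we will recruit 30 individuals per treatment group", and the allowance "With a conservative estimated dropout of 20% across conditions". Section F does not give the separate a and b paths, or the scale on which 0.25 is measured.

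**The concern.** A standard error is a sufficient summary of uncertainty only if the estimate is roughly normal. A product of two estimated coefficients is not normal at this sample size: when both paths are positive it is skewed to the right, and its standard error grows with the estimate. A symmetric interval of 1.96 standard errors then reaches too far towards zero, and a real indirect effect can fail a test that an interval following the shape of the bootstrap distribution would pass.

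At stake is power in an analysis with little to spare. Its purpose is to indicate which mechanisms deserve further study, so a needlessly conservative test may discard a useful mediator. The better interval comes from the same bootstrap draws.

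**Working it through.** **Inputs from the plan.** a*b = 0.25; alpha 0.05 (sidedness not stated, two-sided assumed); power 0.80; 30 per arm; 1:1 allocation (section D); 20% dropout. Hence N = 60, or 60 x 0.80 = 48.

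Both sizes are shown because it is unclear which one section F used. Its companion figure d = 0.72 matches 30 per arm two-sided with no dropout: (1.960 + 0.842) x sqrt(2/30) = 0.723. It also matches 24 per arm one-sided: (1.645 + 0.842) x sqrt(2/24) = 0.718. With 24 per arm two-sided, the same formula gives 2.802 x sqrt(2/24) = 0.81.

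**Assumed.** The split of 0.25 into a and b, and the scaling: either treatment coded 0/1 with unit residual SD, or fully standardised paths. Individuals are independent and errors normal.

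**Step 1: the plan's own figure.** Whether 80% power at a*b = 0.25 is reached depends on the unstated inputs.
- Fully standardised paths, N = 48: the bootstrap-SE test has 59-80% power, reaching 80% at a = 0.45, b = 0.556. In a balanced two-arm trial a standardised path of 0.45 means d = 2a/sqrt(1 - a^2) = 0.90/0.893 = 1.01 on the mediator.
- 0/1 coding: 14-24% at N = 48 and 19-36% at N = 60.

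**Step 2: skewness.** With 0/1 coding, var(a) = 4/N and var(b) = 1/(N - 3). At N = 48 these are 0.0833 and 0.0222, with product 0.00185. For independent normal estimates:
- variance of a*b = a^2 var(b) + b^2 var(a) + var(a) var(b)
- skewness = 6ab var(a) var(b) / variance^1.5

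For a = 0.72, b = 0.347: variance = 0.01152 + 0.01003 + 0.00185 = 0.0234, so skewness = 0.00278/0.00358, about 0.77. For a = b = 0.5: variance = 0.00556 + 0.02083 + 0.00185 = 0.0282, so skewness is about 0.59. The 2.5 and 97.5 percentiles lie at -1.55 and +2.30 SD in the first case and -1.67 and +2.24 SD in the second, not at +/-1.96.

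**Step 3: power at a*b = 0.25.** Simulated trials (2,000-6,000 per scenario, 1,000 bootstrap draws each), with both tests on the same draws: |a*b/SE_boot| > 1.96 against the 2.5-97.5 percentile interval excluding zero. Monte Carlo error is about 1 point.

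| Scaling | a / b | N | SE test | Percentile | Loss (points) |
|---|---|---|---|---|---|
| 0/1 | 0.50 / 0.50 | 48 | 20% | 35% | 15 |
| 0/1 | 0.64 / 0.39 | 48 | 21% | 41% | 20 |
| 0/1 | 0.72 / 0.347 | 48 | 22% | 42% | 20 |
| 0/1 | 1.0 / 0.25 | 48 | 22% | 36% | 14 |
| 0/1 | 0.30 / 0.833 | 48 | 14% | 19% | 5 |
| 0/1 | 0.50 / 0.50 | 60 | 28% | 45% | 17 |
| 0/1 | 0.72 / 0.347 | 60 | 36% | 57% | 22 |
| 0/1 | 0.30 / 0.833 | 60 | 19% | 23% | 4 |
| Standardised | 0.30 / 0.833 | 48 | 59% | 61% | 2 |
| Standardised | 0.45 / 0.556 | 48 | 80% | 90% | 10 |
| Standardised | 0.50 / 0.50 | 48 | 77% | 88% | 10 |
| Standardised | 0.50 / 0.50 | 60 | 90% | 95% | 5 |

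Losses are differences of unrounded rates. Over all standardised splits tried, the loss was about 2-11 points at N = 48 and 2-6 at N = 60.

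**Step 4: type I error, 0/1 coding, N = 48.**

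| a / b | SE test | Percentile |
|---|---|---|
| 0 / 0.347 | 0.8% | 2.8% |
| 0 / 0.5 | 2.0% | 4.9% |
| 0.72 / 0 | 1.4% | 4.2% |
| 1.0 / 0 | 2.8% | 6.2% |
| 0 / 0.8 | 4.5% | 6.5% |

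With both paths null (N = 60) the rates are 0.1% and 0.3%. Most of the percentile interval's gain is recovered conservatism. Where the non-null path is large, the percentile interval is mildly liberal, at about 6-7.5% across repeated runs.

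**The case against.** The wording names neither a z-test nor a reference distribution. It may be loose phrasing for a bootstrap interval, and the method source it cites cannot be consulted here. That stands: the normal reference is the natural reading, not the plan's words. The same sentence would settle the matter either way.

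A reader might infer a general loss of about 20 points. The documents do not support this. They give no paths and no scaling, and the scaling under which the planned test comes near section F's 80% is the standardised one, where the loss is at most about 11 points. For the same reason, the low powers under 0/1 coding do not show section F's statement to be wrong.

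A reader might also infer that the bootstrap ignores randomisation in units of up to three. The plan does not say what is resampled. In a check with everyone in triplets and an assumed intraclass correlation of 0.1, resampling whole units did not improve the percentile interval's type I error: 7.9% against 7.4% for individuals at a = 0, b = 0.5, and 5.2% against 4.0% at a = 0.72, b = 0. Unit resampling would respect the design, but it has no demonstrated gain.

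Finally, the analysis is exploratory, its low power is admitted, and a conservative test does not inflate false claims of mediation. This limits the consequence. The admission follows the GLMM text, however, and does not justify the choice of test.

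**Conclusion.** The point holds as a minor one. Read naturally, the planned GLM test is usually conservative and gives up power for no benefit beyond that conservatism. The size of the loss, about 2 to 22 points at a*b = 0.25, is an assumption-dependent range and not a property of the plan: the upper end needs 0/1 coding with a roughly between 0.6 and 0.8, and the lower end comes with unbalanced or standardised paths. In every scenario run at a*b = 0.25 the percentile interval had the higher power. The figures rest on two-sided testing and independent individuals with normal errors. The Aim 1 outcomes and the Aim 2 treatment comparisons are not affected.

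**What to change.** In Specific Aim 2, Exploratory Hypothesis, replace the sentence on the GLM mediation test with wording such as: *Exploratory GLM indirect effects will be reported and tested with a 95% percentile bootstrap confidence interval based on at least 5,000 resamples, in place of a normal-theory test on the bootstrap standard error.* The percentile interval is preferable to the bias-corrected one here, because the latter's type I error reached about 9% in the same simulations. The sentence may also name the resampling unit, as a matter of respecting the design.

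The cost is one sentence, no extra data and negligible computing. The price is the mildly liberal error rate when one path is null and the other large, which should be acknowledged when results are reported.

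### The 2-1-1 mediation model has one mediator slope that mixes between-person and within-person association, so its indirect effect can be understated or spurious when the two differ

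*Combined protocol and SAP*

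**What the plan says.** Section G, Specific Aim 2, Exploratory Hypothesis, proposes that changes in negative beliefs, connectedness and forgiveness mediate the effect of treatment on changes in PTSD and related symptoms. Two analyses are planned.

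- **GLM.** The Session 3 mediator is predicted from treatment, and the follow-up outcome from that mediator, adjusting for treatment and baseline.
- **GLMM.** The 2-1-1 model is set out as "predicting the mediator at all time points from treatment (2-1), and the outcome at all time points from the mediator (1-1), controlling for treatment", which follows a cited methodological paper and is described as "generally following the product of coefficients method".

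Neither this text nor the Specific Aim 1 model it builds on mentions person-mean centring, a person mean as a second predictor, or separate within- and between-person slopes. Specific Aim 1 allows random coefficients for time-varying covariates. These let slopes vary across people but do not separate the two kinds of slope.

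Section F bases the repeated-measures work on four assessments: "with 4 data points, 30 per group with 20% missing data". It says of the mediation that "tests of indirect effects are exploratory", and gives 0.25 as the indirect effect the study can detect. The Exploratory Hypothesis text ends: "It is recognized that this is underpowered". Section D places the first assessment before Session 1, then Session 3, Session 6 and three months.

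**The concern.** The a path compares arms, so it is a person-level effect. The b path is one slope on the raw visit-level mediator. In a random-intercept model that slope blends two associations. One is between people: those with lower average PTCI scores have lower average PTSD scores. The other is within people: at visits when a person's PTCI score is below their own usual level, so is their PTSD score. These need not be equal, and the product of coefficients gives no sign of which one drove it.

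At stake is the reading of mechanism. A real indirect effect could be reported as much smaller than it is, or one could be reported where treatment-induced change in the mediator does nothing. This is bias, so a larger sample would not remove it, and the admission of low power does not cover it.

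**Working it through.** **The plan's own figure.** Section F gives a detectable a × b of 0.25 at alpha 0.05 and power 0.80, but neither its metric nor its split into a and b. With a as a standardized difference, joint-significance power peaks at 0.49 (24 per arm) or 0.64 (30 per arm). On a correlation scale with a = b = 0.5 it is 0.90 (N = 48) or 0.96 (N = 60). The figure can be neither confirmed nor refuted, and serves here only as a yardstick of size.

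**Weight of the within-person slope.** With T visits, mediator ICC *m* and residual outcome ICC *y*:

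- W = (T − 1)(1 − m)/(1 − y)
- B = [m + (1 − m)/T]/[y + (1 − y)/T]
- within-person share = W/(W + B)

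From the documents, T = 4. If m = y, then W = 3 and B = 1, so the share is 3/4 = 75%.

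The documents give no ICCs. As stand-ins for m, take the retest correlations in Section C, with y assumed to lie between 0.3 and 0.8:

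| Mediator (retest r) | Within-person share |
|---|---|
| Social Connectedness (.96, two weeks) | 8–34% |
| DSES (.85, two days) | 26–68% |
| PTCI (.74) | 40–80% |
| TRIM-R (.83, three weeks) | 28–71% |
| TRIM-R (.44, eight weeks) | 66–92% |

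Lowest end: W = 3 × 0.04/0.7 = 0.171; B = 0.97/0.475 = 2.042; share = 0.171/2.213 = 8%. Highest end: W = 3 × 0.56/0.2 = 8.4; B = 0.58/0.85 = 0.682; share = 8.4/9.082 = 92%.

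**Effect on the product.** Simulation with a random intercept and visit dummies: 60 people, four visits, complete data, no treatment-group or randomization-cluster effects, 300 replicates. Assumed values: both ICCs 0.5, full treatment effect on the mediator 0.72, non-zero slopes 0.5. Where the effect starts after baseline it follows the pattern 0, 0.5, 1, 1. The average a is then 0.72 × 0.625 = 0.45, and the true path, where there is one, is 0.45 × 0.5 = 0.225.

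| Scenario | True a × b | Single slope (planned) | a × person-mean slope | a × within-person slope |
|---|---|---|---|---|
| 1. Effect at all visits, carried between people; within slope 0 | 0.36 | 0.064 | 0.291 | −0.001 |
| 2. Effect at all visits, no treatment path; within slope 0.5 | 0 | 0.300 | 0.080 | 0.364 |
| 3. Effect after baseline, path equals between slope; within slope 0 | 0.225 | 0.047 | 0.175 | 0.012 |
| 4. Effect after baseline, no treatment path; within slope 0.5 | 0 | 0.182 | 0.051 | 0.219 |
| 5. Effect after baseline, path runs through within-person change; between slope 0 | 0.225 | 0.196 | 0.048 | 0.236 |
| 6. Effect after baseline, equal slopes | 0.225 | 0.233 | 0.229 | 0.235 |

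With 48 people (20% loss) the single-slope product is 0.062 in scenario 1 and 0.296 in scenario 2. In scenario 2 both paths are significant in 90% of runs, against 13% with the person-mean slope.

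The formula can be checked against scenario 1. The fitted single slope was 0.086 and the person-mean slope 0.390, with a within slope near zero. The implied within-person share is 1 − 0.086/0.390 = 78%, close to 75%.

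The distortion shrinks when the mediator is much more stable than the outcome. With 48 people, m = 0.96 and y = 0.5, scenario 1 gives 0.299 of 0.36 (83%) and scenario 2 gives 0.044.

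**What the split can and cannot show.** Scenarios 4 and 5 give nearly the same three products but have opposite truths. The split shows that the two slopes disagree. It does not show which one treatment acts through.

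**The case against.** The strongest objection concerns the remedy. A reader might infer that the person-mean product is the correct 2-1-1 indirect effect and that the within-person slope is only visit-to-visit covariation. The documents do not support this. The hypothesis is about changes, and the first assessment precedes treatment, so a treatment effect shows up as change within people. In scenario 5 the planned slope (0.196) is far closer to the truth (0.225) than the person-mean product (0.048). Dropping baseline does not reverse this. With 48 people the true path becomes 0.72 × (0.5 + 1 + 1)/3 × 0.5 = 0.30; the planned model gives 0.23 and the person-mean product 0.09. Randomization also does not protect the b path from stable traits. Where such traits correlate across people but treatment-induced mediator change does nothing, the person-mean product was 0.18 with both paths significant in 40% of runs, against 0.04 and 10% for the planned slope. This objection stands and shapes the fix.

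The cited paper may deal with centring, which cannot be checked here. The plan's own wording does not, so a sentence is needed either way.

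The retest values put several mediators at low within-person shares. That is fair, but they come from the original forms over intervals from two days to eight weeks. The trial uses brief or adapted versions of several scales and runs through six weekly sessions plus three months. Stability in the trial may be lower.

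Finally, the analysis is exploratory, and the parallel GLM uses one mediator value per person, so it has no mixing. Both points limit the consequence. However, the plan gives no rule for the case where GLM and GLMM disagree.

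**Conclusion.** The point holds in a limited form. The GLMM mediation as written multiplies a person-level effect by a blended slope. If the between- and within-person slopes are equal there is no bias. If they differ, the product can understate an indirect effect or show one that does not exist, and the simulated errors approach the size of the plan's own 0.25.

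A reader might go further and infer that the slope is about 80% within-person, so that the indirect effect appears at a fifth of its size. The documents do not support that as a general statement. The share is 75% with equal ICCs and ranges from roughly 8% to 92% on the retest proxies. A fifth needs an 80% share and a within-person slope of exactly zero. At that share, a within slope half the between slope leaves 0.2 + 0.8 × 0.5 = 60%, and equal slopes leave 100%.

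The sizes rest on assumed ICCs, slopes and effect patterns. The primary PTSD comparison is untouched. The change is worth making, but the consequence is confined to an exploratory analysis.

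**What to change.** In the 2-1-1 outcome model, enter the mediator as two terms, the person's mean and the visit's deviation from that mean, and report both slopes. State which visits the mean covers. Then prespecify two products, reported side by side:

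- **Person-level:** treatment effect on the post-baseline mediator mean, times the person-mean slope.
- **Change-based:** treatment-by-time effect on the mediator, times the within-person slope.

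Add that neither is the default and that no mediation will be claimed from the blended slope when the two disagree. Say also what each relies on. The person-level product assumes that stable traits do not confound the slope. The change-based product assumes that visit-to-visit association also applies to change caused by treatment.

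The cost is one extra fixed effect, a few sentences in the analysis plan and less precision. In simulation with 48 people, the standard deviation of the indirect effect was about 0.09–0.15 with the person-mean slope, against 0.05–0.13 with the single slope. No new data are needed.
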